4.5 Study procedures

Screening

Initial screening of study participants will be done by the research assistant on patients admitted to the ICU. Expectation of a length of stay >24 hours will be discussed with the treating team. If a patient fulfills inclusion criteria the research assistant will perform the consenting procedure with the patient or with the primary caregiver in case the patient is unconscious or unwell. After informed written consent is obtained from the patient or primary caregiver, the patient will be recruited in ICOPE.

Recruitment

Once eligibility is confirmed, the study will be explained to the patient or their primary caregiver. The research assistant will then conduct the consent procedure, which involves providing information about the study through the participant information sheet and obtaining written informed consent. Any reasons for exclusion, such as refusal to provide informed consent, will be recorded in the 'Screening and Enrolment Log'. After obtaining consent, the patient will be enrolled in the study.

Informed Consent

The participant or legally authorized person or primary caregiver must personally sign and date the latest approved version of the Informed Consent Form (ICF) before any study interview is performed. A written version of the Participant Information Sheet (PIS) and ICF will be presented and verbally explained to the patients, legal guardian or primary caregiver. Written Informed Consent will be obtained by means of participants (or witness if illiterate) dated signature (or thumb print plus dated signature of literate witness if legal guardian/primary caregiver unable to write) and a dated signature of the person who presented and obtained the Informed Consent. A copy of the signed Informed Consent will be given to the participant.

4.6 Data to be collected

CRF structure and timeline is detailed in **Table 1** and comprises sequential domains from A to F. Daily follow up will run until ICU discharge or death, whichever occurs first. An additional telephone follow up at 30 days and 6 months will be used in survivors.

Table 1. CRF structure and timepoints for data collection

	ICU Admission day	Daily (max every 72h)	ICU Discharge	30 days	6 months	Responder
A Socioeconomic status and admission costs	X					Patient or caregiver
B Relative Wealth tool	X					
C Costs form	X	X				
D Discharge form			X			
E Follow up form				☎	☎	Patient or caregiver (telephone)
F Clinical registry Admission form (core) Daily processes of care Discharge (core)	X	X	X			Extracted from patient file

*In some instances daily followup may not be feasible due to unavailability of family members or unwillingness to discuss the study. Therefore a maximum interval of 72h is granted between two daily forms.

#A. Socioeconomic status and admission costs

Absolute household estimated yearly and monthly income will be collected in order to calculate CHE. Household consumption expenditure (food and non-food expenditure) will also be collected in order to minimize recall bias and potential missing income data. This information on expenditure will be used as a proxy of income, in cases where the income information is missing.

The following potential risk factors for CHE will be investigated: household income status, patient occupation; marital status; religion; access to safe water; educational status; ownership and location of households (urban vs. rural vs. slum); female-headed households; household size and age/gender of members; geographical location.¹⁰

#B. Relative wealth

Relative wealth will be quantified using the Equity tool (www.equitytool.org), consisting of a short survey of 11-12 questions allowing to compare the wealth of the respondents to the national or urban population in over 60 countries.

#C. Costs form

Granularity on direct medical and non-medical costs will be sought. Family members (supported by research assistants) will be asked to provide information about expenditure on each visit to ICU. The data collection will ideally be daily, but time window is extended to maximum every 72h as we acknowledge several barriers to daily collection e.g. family members may not visit each day, the research assistant may face conflictual family meetings and some family members assisting a severe kin may not be comfortable with a daily visit. The form will be administered until patient discharge from ICU or death, whichever occurs

first. Direct medical and direct non-medical costs categories and operational definitions are defined in **Appendix 1**.

#D. Discharge form

The discharge form will comprise ICU and hospital discharge outcome and the MRC and EQ5D-3L functional outcome status. The EQ5D-3L is validated to monitor changes in self-reported health status through time in a given patient group.²³

#E. Follow up form

The follow-up form to be collected by telephone outreach will contain the vital status, EQ5D-3L functional outcome status. The telephone version of EQ5D-3L will be used.²⁴

#F. Registry variables

Patient characteristics, severity of illness, case-mix information and outcomes will be captured using the existing Critical Care Asia Africa (CCAA) network core registry data set. This dataset contains the following features on *admission*: demographics information, reason of admission, severity score on admission (eTROPICs and/or SOFA and/or APACHE II) and comorbidities. Clinical data points collected *daily* include variables used for the derivation of process-measures, organ support features and quality indicators. The following data will be collected:

- ventilation status and execution of spontaneous breathing trials;
- sedation status;
- use of renal replacement therapy;
- use of cardiovascular support such as vasopressors or inotropes;
- use of deep venous thrombosis prophylaxis and stress ulcer prophylaxis;
- infection and antimicrobial treatment status i.e. documented infections and number of antibiotics received during stay.

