4.8 Statistical analysis

Normally distributed continuous variables will be summarized using means and standard deviations while ordinal variables and skewed continuous data will be expressed as median with interquartile range. For categorical variables, percentages will be calculated and tests of significance between categorical variables will be done using a Fisher's exact or a Chi-square test as appropriate. Student's t-test will be used to compare normally distributed numerical variables between factors and a linear regression model will be fitted where applicable. Mann Whitney U-tests and Kruskal-Wallis tests will be used to compare numerical variables when normality cannot be assumed.

Analysis of the primary endpoint

a. Quantification of ICU OOPes

The primary endpoint will be summarized by reporting overall income group quintiles. Information on direct medical costs, including ICU bed charges, laboratory costs, medication

costs, procedure costs, consumables, medical nutrition, and other related costs will be obtained and summarized.

b. Calculation of CHE

The best method for CHE calculation for single patient episodes is debated in the literature. For the purpose of this study ICU episodes causing CHE will be defined as the calculated total episode OOPE divided by total *yearly* household income exceeding **10%**.²

Other applicable definitions that are justified in literature will also be considered and clearly documented in the Statistical Analysis Plan prior to statistical analysis.

c. CHE Sensitivity analysis

The primary analysis regarding CHE will be repeated using a variety of other considerations as a form of sensitivity analysis. These sensitivity analyses will be clearly outlined in the Statistical Analysis Plan prior to database lock and statistical analysis.

Analysis of risk factors for CHE

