10. APPENDIX

Appendix 1. Operational definitions

Term	Definition
OOPE	Defined as the cost incurred by individuals or households at the time of receiving any healthcare services in the ICU, including the component of cost-sharing (the part not covered by a third party like, an insurer) and informal payments (e.g., tips and under-the-table payments), but excluding insurance premiums and any reimbursements from the third-party payers (e.g., the government, a health insurance fund or a private insurance company). OOPE includes direct medical and direct non-medical costs, but excludes indirect costs (such as income/productivity loss).
Catastrophic health expenditure (CHE):	For CHE incidence estimation, there is no single agreed threshold. In this study CHE will be defined as OOPEs exceeding 10% of the household budget (yearly income or consumption expenditure). In sensitivity analysis, we will apply the higher threshold level of 25%.
Direct costs	Direct costs are expressed as expenditure during ICU treatment by households and consist of two main categories: direct medical cost and direct non-medical cost.
Direct medical costs	Subcategory of 'direct costs' referring to direct payments made by individuals to healthcare providers at the time of service use. These include those costs that are consumed for healthcare resources during ICU care and will be classified across 7 categories. 
 - Facility/provider fees, e.g. ICU bed charges, hospital daily rates, theater fees. - Laboratory costs - Medication costs e.g. drugs, fluids, nutrition solutions, bandages - Procedure costs e.g. diagnostic imaging procedures, mechanical ventilation, dialysis - Consumables e.g. (ventilator circuits, infusion sets, ventilation masks, gloves, alcohol rub, etc.) - Medical nutrition - Other costs These exclude any prepayment for health services, for example in the form of taxes or specific insurance premiums or contributions and where possible, net of any reimbursement to the individual who made the payments.
Direct non-medical costs	Subcategory of 'direct costs' including transportation, lodging, food items, informal payments and tips, payments incurred by caregivers and family for helping the patients during treatment.

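### Estimated household income is both the denominator of CHE and a tested risk factor for CHE, so its estimated effect is partly definitional and partly shared reporting error

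*Protocol*

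**What the plan says.** Protocol section 4.6, part A, explains why income is collected: "Absolute household estimated yearly and monthly income will be collected in order to calculate CHE". Where it is missing, consumption expenditure stands in: "This information on expenditure will be used as a proxy of income, in cases where the income information is missing". Section 4.8 b sets the outcome as "the calculated total episode OOPE divided by total *yearly* household income exceeding 10" per cent. Appendix 1 is slightly wider: "In this study CHE will be defined as OOPEs exceeding 10% of the household budget (yearly income or consumption expenditure").

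The same part of section 4.6 lists the candidate predictors, with income first: "The following potential risk factors for CHE will be investigated: household income status, patient occupation; marital status; religion". Section 4.4 makes risk factors for CHE a secondary endpoint, points to that list and calls it presumptive. Section 4.8 puts the risk factors into a multivariable mixed-effects logistic model with ICU and country levels, tested at 5%.

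Part B of section 4.6 adds a second socioeconomic measure: "Relative wealth will be quantified using the Equity tool". It is scheduled on the admission day and compares the household with its national or urban population. Section 4.8 gives it no role, and the risk-factor list does not name it.

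For costs, section 4.8 a says: "The primary endpoint will be summarized by reporting overall income group quintiles". It does not state whether these quintiles are pooled over countries, formed within country or taken from a national reference, nor in which currency.

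**The concern.** If income is over-reported, the ratio of OOPE to income falls while the income covariate rises; if it is under-reported, the reverse happens. The two are then inversely associated even where true income has no bearing on CHE. Section 4.6 itself makes such error plausible: income is estimated, a caregiver may answer, and recall bias and missing income are the stated reasons for also collecting expenditure.

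The second aim of the study is to identify risk factors for CHE. A low-income effect could be reported as an independent empirical finding when part of it is arithmetic. Factors that track true income, such as education, occupation and location, would absorb some of the distortion. The random effects for ICU and country do not remove this, because the overlap arises within the household.

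**Working it through.** The protocol gives no figure to reproduce here, so the check is algebra followed by simulation.

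**Inputs from the protocol.** CHE threshold 10% (section 4.8). Expected CHE 30% in ventilated and 15% in non-ventilated patients, with 40% ventilated (section 4.3), so overall CHE = 0.4 × 30% + 0.6 × 15% = 21%. Evaluable sample 307 and at least 5 countries (section 4.3).

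**Assumed inputs, not in the protocol.** SD of true log income 0.9. SD of log(OOPE/income) 1.2 when OOPE is proportional to income. SD of log reporting error 0.3, 0.5 or 0.7. Wealth index = log income plus independent error of SD 0.7.

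**Algebra.** Let L be true log income and L + u reported log income, and let log OOPE = a + βL + e. CHE occurs when a + (β − 1)L − u + e > log 0.10. The covariance of the left-hand side with reported log income is (β − 1)·Var(L) − Var(u).

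- The first term is definitional and real: it vanishes only if bills rise in proportion to income (β = 1).
- The second term is pure reporting error and is always negative.

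At β = 1 and error SD 0.5, the slope of the log ratio on reported log income is −0.25/(0.81 + 0.25) = −0.24, although the true slope is zero. For a wealth index with independent error, the second term drops out, but the first is shrunk by 0.81/(0.81 + 0.49) = 0.62.

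**Error component alone (β = 1, true gradient zero).**

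| Error SD | Odds ratio, lowest vs highest reported-income fifth | Adjusted odds ratio of an education factor with no true effect | Rejection rate at n = 307, 5% test of income |
|---|---|---|---|
| 0 | 1.0 | – | 4.8% |
| 0.3 | about 1.5 | 1.2–1.3 | 16% |
| 0.5 | about 2.5 | 1.5 | 65% |
| 0.7 | about 5 | 1.9 | 97% |

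At SD 0.5, CHE is 31% in the lowest and 15% in the highest reported-income fifth: (0.31/0.69)/(0.15/0.85) = 2.5. With the wealth index in place of income, both odds ratios stay at about 1.0. A second set of assumptions (SD of log income 0.6–1.0, SD of log OOPE net of income 1.0–1.3, error SD 0.4) gives spurious gradients from 25.7% versus 16.7% up to 29.7% versus 13.3%.

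**Definitional component alone (β = 0, no error).** Under that second set, CHE runs from 40.5% in the poorest to 6.7% in the richest fifth in the mildest case, and from 58.8% to 0.9% in the steepest. This is the definition at work and not an error.

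**Both components (β = 0.5, error SD 0.5).** The true odds ratio is about 6. Reported income gives 13 and the wealth index 3.7. With the wealth index in the model, the null education factor moves to about 0.7, and to about 0.5 at β = 0, because income is incompletely adjusted for.

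**Quintiles, if pooled.** With 5 equal-sized countries, between-country SD of log income 0.3–1.0 and within-country SD 0.6–1.0, the largest single country fills on average 31–62% of an extreme quintile, against 20% with no sorting. Country explains 7–60% of the variance in log income.

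**The case against.** The strongest reply is that CHE is meant to measure spending against means. A poorer household facing a similar bill does have more CHE, so an income gradient is expected and informative. This stands. A reader might infer that the whole gradient is artefact; the documents do not support that, and the null case β = 1 was chosen only to isolate the error term. The protocol fixes neither how bills scale with income nor how large the reporting error is.

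A reader might also infer that the quintiles mainly sort patients by country. That is not established. Section 4.8 a does not fix the reference population, the between-country income spread is not in the document, and the sentence concerns costs rather than CHE. Section 4.4 also reports costs in purchasing-power-parity dollars, which lessens the price-level part of the worry.

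Third, the Equity tool is not free of bias. It attenuates a true gradient, leaves residual confounding by income, and if half of the income-reporting error carried over to it, it would itself show a spurious odds ratio of about 1.5. Coverage of every study country is not confirmed in the protocol. This stands against replacing income outright.

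Fourth, covariate coding and the role of the wealth form may be settled in the SAP, which is not shown, and the list is called presumptive. This is fair as far as it goes, but the overlap itself is written in the protocol: income is named both as the denominator and as a candidate predictor.

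Finally, expenditure data, other CHE definitions and sensitivity analyses are planned. These help with the outcome, but where expenditure replaces income the same coupling can run through the proxy.

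**Conclusion.** The point holds for the secondary risk-factor analysis. Using estimated income as both denominator and predictor yields an association that combines a genuine definitional part with a further inverse part from reporting error. The second part alone amounts to an odds ratio of about 1.5 to 5 between extreme fifths for log-error SD 0.3 to 0.7, if OOPE is proportional to true income, and it can make an inert correlated factor look active. These sizes depend on assumed SDs; the direction does not, as long as income is reported with error unrelated to true income and to OOPE.

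The point does not extend to the primary contrast of ventilated with non-ventilated patients, for which the protocol specifies no income covariate. For the cost summary, all that can be said is that pooled quintiles could partly sort patients by country; how strongly cannot be judged from the document.

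**What to change.** In sections 4.6 and 4.8:

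1. Name the Equity-tool wealth quintile (form B) as the socioeconomic risk factor in the main CHE model.
2. Report the same model with household income as a sensitivity analysis, and show both side by side.
3. Present the income–CHE gradient as descriptive and partly definitional, not as an independent risk factor.
4. State that income quintiles for the cost summary are formed within country, or use Equity-tool quintiles.

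The cost is wording and one additional model; the form is already scheduled at admission, so no new data are needed. The drawback is that the index measures assets rather than cash income, attenuates a true income gradient and may leave some confounding by income. Neither model is sufficient alone, which is why both should be reported.

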1. STUDY SUMMARY

Title	ICU-related Out of Pocket Expenses (ICOPE) – a multinational prospective study in African and Asian countries		
Sponsor	Mahidol Oxford Tropical Research Unit Collaboration for Research, Implementation and Training in Critical Care in Asia and Africa (CCAA)		
Funder	Wellcome		
Trial design	Prospective observational study		
Trial Participants	All patients admitted to the participating ICUs during a predefined window of 14 days and expected to have a duration of stay >24 hours. Exclusion criteria is lack of informed consent.		
Sample size	at least 354 patients (at least 212 non-ventilated & 142 ventilated patients)		
Planned study period	Recruitment during 14 days Follow up until ICU discharge for each recruited patient, at 30 days after admission and 6 months after admission. Total study duration: 18 months		
Planned recruitment period	From 01 Dec 2023 to 30 June 2024		
	Objectives	Endpoints	Timepoint(s) of evaluation
Primary objective	To quantify ICU care related OOPE in African and Asian LMICs and the proportion of patients/families facing CHE, comparing patients receiving invasive ventilation to non-ventilated patients.	1.Costs per complete patient episode, as actually spent in US dollars and International dollars (purchasing power parity exchange rate) in ventilated versus non-ventilated groups. 2.Relative risk of CHE in ventilated versus non-ventilated groups.	During ICU stay, average 1 week
Secondary objectives	To identify risk factors for CHE.	Risk factors for CHE	Not applicable
	To identify coping strategies for OOPE and CHE	Frequency of different coping strategies for financial coverage of ICU costs	During ICU stay and follow up, 6 months

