3.2 Hypothesis

The following exploratory hypothesis are formulated:

- Mechanical ventilation has a doubling effect on CHE incidence.
- The risk of CHE and magnitude of OOPE can be predicted by distinct patient-, disease-, household- and organizational-related factors.
- Distress financing by borrowing from family members is the most frequent coping mechanism both in Asia and Africa.

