4.4 Study parameters/endpoints

Primary endpoints:

- Costs per complete patient episode, as actually spent in US dollars and International dollars (purchasing power parity exchange rate) in ventilated versus non-ventilated groups.
- Relative risk of CHE in ventilated versus non-ventilated groups.

Secondary endpoints:

- Risk factors for CHE (presumptive list in section 4.6)
- Frequency of different coping strategies for financial coverage of ICU costs

Tertiary endpoints

- Proportion of direct medical versus direct non-medical costs in the total OOPes
- Patient family socio-economic status (SES) or income
- Paying structures, models by country.

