Yearly/ Annual Income	Annual income refers to the total amount of money earned by a household over the course of a year (i.e. last 12 months preceding this survey time). This income can come from various sources, such as salary or wages from employment, profits from a business, rental income, investment income, land, or any other source of income received over the course of a year.
Yearly/ Annual Expenditure	Annual expenditure refers to the total amount of money spent by a household over the course of a year (i.e., last 12 months preceding this survey). This includes all expenses such as rent or mortgage payments, utilities, groceries,

	transportation costs, insurance, taxes, entertainment, food and any other expenses incurred during the year.
Family caregivers	
Defined as any family member, relative, partner or friend of the ICU patient, who were caring for the patient while he or she stayed in the ICU with or without remuneration.
 
- Primary family caregiver: is the family caregiver with the most patient contact.- Secondary family caregivers: defined as any other family member or friend over the age of 18 involved in patient care and listed along with their time commitment by the primary family care-giver.
Coping strategies	
Any mechanisms for OOPE coverage by patient or family member, including:
 
- Savings: own income.- Medical debt: defined as personal debt derived from healthcare expenditures or paying for medical OOPE by borrowing money from friends or family, institutional loans (banks, etc) or non institutional loans (borrowing from black market).- selling of personal property- limitation to procurement of medical services or drugs- other

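### Coping strategies are an endpoint up to 6 months, but the only form used after ICU discharge is not described as recording them

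*Protocol*

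**What the plan says.** Identifying coping strategies is the third aim in section 3.1. Section 4.4 makes it one of two secondary endpoints: "Frequency of different coping strategies for financial coverage of ICU costs". No timepoint is attached there. The study summary supplies one: "During ICU stay and follow up, 6 months".

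Section 4.6 describes forms A to F. On the post-ICU contacts it says "An additional telephone follow up at 30 days and 6 months will be used in survivors", and on the form used for them, "The follow-up form to be collected by telephone outreach will contain the vital status, EQ5D-3L functional outcome status". Table 1 lists the patient or a caregiver as the telephone responder for that form. On form D: "The discharge form will comprise ICU and hospital discharge outcome and the MRC and EQ5D-3L functional outcome status".

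Section 3.2 states an exploratory hypothesis: "Distress financing by borrowing from family members is the most frequent coping mechanism both in Asia and Africa". Appendix 1 defines the coping strategies as savings, medical debt, selling property, limiting the services or drugs procured, and other. Borrowing from family falls within medical debt, which covers "borrowing money from friends or family, institutional loans (banks, etc) or non institutional loans".

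**The concern.** The endpoint has a stated timepoint that none of the described forms serves. This concerns data collection and not analysis, so a statistical analysis plan that is not shown here could not repair it. Once the 30-day and 6-month calls have been made without the question, the information is lost or depends on late recall.

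Two related matters affect how a repair should be made. Coping is a household matter: Appendix 1 defines it as action by the patient or a family member, and a loan or a sold asset outlasts the patient's death. A coping item added to form E with the survivor limit unchanged would leave out bereaved households after ICU discharge. And the hypothesis is about family borrowing, while the defined category also holds friends, banks and black-market lenders.

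**Working it through.** No figure is in dispute, and the endpoint has no stated sample size, power or significance level, so there is nothing to recompute. The check sets the endpoint's timing against the forms.

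**Step 1: what each form is described as holding (section 4.6 and Table 1).**

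| Form | When | Described content | Coping named? |
|---|---|---|---|
| A | Admission | Income, consumption expenditure, household characteristics | No |
| B | Admission | Relative wealth survey | No |
| C | Admission, then daily (at most 72 h apart) to ICU discharge or death | Medical and non-medical expenditure | No |
| D | ICU discharge | Discharge outcome, MRC, EQ5D-3L | No |
| E | 30 days, 6 months | Vital status, EQ5D-3L | No |
| F | Admission, daily, discharge | Clinical registry data from the patient file | No |

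**Step 2: the post-ICU part.** Table 1 schedules only form E after ICU discharge. (The text on form D also mentions hospital discharge outcome, but no financing item.) Form E has two contacts, and its described content includes coping at neither. As described, coping is collected at 0 of 2 post-ICU contacts, for 0% of households, against a stated timepoint of 6 months.

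**Step 3: the ICU part.** Form C is an interview about spending that runs until ICU discharge or death, so there is an occasion on which coping could be asked, including in households whose patient dies in the ICU. The protocol does not say that it is asked there or on any other form. This is an omission of the form's name, not evidence that collection is impossible.

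**Step 4: the survivor limit.** With form E as described, the limit removes no coping data, because none is collected on it. It matters once a coping item is added: households whose patient is known to have died before a call would not be asked. EQ5D-3L needs a living patient and a coping question does not. Table 1 already allows a caregiver to answer.

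**Step 5: the category.** Let F be the share of households borrowing from family and M the share with any medical debt, so F ≤ M. Suppose responses were recorded only as the five terms in Appendix 1. If another term exceeded M, it would also exceed F and the hypothesis would be contradicted. If M ranked first, F could lie anywhere from 0 to M, and the hypothesis would be neither confirmed nor refuted. Whether responses are pooled in this way depends on the response list in the case report form, which the protocol does not reproduce.

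**The case against.** The best reply is that section 4.6 summarises the forms and does not reproduce them. It says what form E will contain and does not say that nothing else is on it. The summaries are visibly incomplete: form A has admission costs in its title, but its description lists no such item. Appendix 1 gives an operational definition of coping strategies, which suggests that collection is intended, and section 4.7 says that a stakeholder group reviewed the forms. A coping item may therefore exist. That stands as a limit on certainty. It does not remove the inconsistency: if form E does carry the item, its description is incomplete on a secondary endpoint and needs correcting.

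It can also be said that section 4.4 sets no 6-month horizon and that section 2.3 speaks of borrowing and selling assets during ICU care. This is fair, and it supports shortening the timepoint as an acceptable repair.

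A reader might infer several stronger things that the protocol does not support:

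- *The endpoint cannot be measured at all.* Only the post-ICU part lacks a described source.
- *The endpoint would describe survivor households only.* In-ICU interviews run to discharge or death, so they can include households whose patient dies there.
- *A count of households never called.* The protocol gives no mortality figure. Form E itself collects vital status, so some deaths would be discovered at a call. Any such count would rest on assumption, as would the idea that the missing households are mostly those of ventilated patients.
- *The family-borrowing hypothesis cannot be tested.* Appendix 1 is a definition that itemises lender types, not a response list. It shows a mismatch to clear up, and no more.

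**Conclusion.** The point holds for the period after ICU discharge. The study summary promises coping data to 6 months, and the only form scheduled after ICU discharge is described without them. Followed as written, the plan yields no post-ICU coping data for any household. For the ICU stay, the collecting form is simply not named. The hypothesis and the medical debt category do not match, which is a reason to record family borrowing separately.

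This rests on taking the description of form E as complete; the case report form pages are not available to check. The matter should be fixed rather than being critical: the endpoint is secondary and descriptive, the hypothesis is exploratory, and neither primary endpoint depends on it.

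**What to change.** 1. Name the form that collects coping strategies, and have it completed for every patient at ICU discharge or death.
2. Add the coping item to form E at 30 days and 6 months, and amend its description in section 4.6.
3. Reword the survivor limit so that it applies to EQ5D-3L, and put the coping item to the caregiver when the patient has died.
4. Record borrowing from family as its own response, separate from friends, institutional lenders and non-institutional lenders.

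If post-ICU coping is not wanted, the minimum alternative to items 2 and 3 is to shorten the timepoint in the study summary to the ICU stay; items 1 and 4 still apply.

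The cost is a few form items, an amendment, matching consent wording, and some short but sensitive calls to bereaved caregivers. The minimum alternative avoids those calls but gives up information on how households coped after ICU discharge. Either change has to precede the contacts concerned.
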